### 7.5.3 Prohibited Concomitant Therapy

- Any investigational drug other than study medication is NOT permitted during the study.
- The concomitant administration of deferasirox and aluminum-containing antacid preparations has not been formally studied. Although deferasirox has a lower affinity for aluminum than for iron, avoid use of deferasirox with aluminum-containing antacid preparations due to the mechanism of action of deferasirox.

## 7.6 Dose Modifications

### 7.6.1 Based on Concomitant Medications

As stated in Section 7.5.1 deferasirox will be adjusted based upon concomitant medications which interferes with metabolism.

### 7.6.2 Change in Patient's Weight

The dose of study medication should be adapted using during the study if the change (increase or decrease) in body weight exceeds 10% of the body weight compared to the baseline visit or the last dose adjustment due to change in patient's body weight

### 7.6.3 Renal Impairment

Serum creatinine and proteinuria should be monitored during the study as stated in Table 2.

Deferasirox can cause acute renal failure, fatal in some patients and requiring dialysis in others. Postmarketing experience showed that most fatalities occurred in patients with multiple comorbidities and who were in advanced stages of their hematological disorders. In the clinical trials, deferasirox-treated patients experienced dose-dependent increases in serum creatinine.

Measure serum creatinine and determine the glomerular filtration rate (GFR, estimated by the MDRD method) before initiating therapy in all patients.

Deferasirox is contraindicated in patients with an estimated GFR less than 40 mL/minute or serum creatinine greater than 2 times the age-appropriate upper-limit-of-normal (ULN). Renal tubular damage, including Fanconi's Syndrome, has been reported in patients treated with deferasirox, most commonly in children and adolescents with beta-thalassemia and serum ferritin levels <1500 mcg/L.

Deferasirox will be administered and dosed at the discretion of the treating clinician based on renal function as measured by serum creatinine and via the estimated GFR.

Intermittent proteinuria of unclear significance was also noted in clinical trials with deferasirox. The level of proteinuria will be measured per Table 2 (at baseline before treatment, at 6 months and again at 12 months) strictly for monitoring. Deferasirox will be administered and dosed at the discretion of the treating clinician based on the

results of monitoring for proteinuria. However, given the intermittent nature of proteinuria experienced with deferasirox and its unclear significance, there is no contraindication to the administration of deferasirox based on level of proteinuria.

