### **2.3 Study Agent**

Patients will receive oral deferasirox which has been approved by the FDA for the treatment of chronic iron overload due to blood transfusions in patients 2 years of age or older. Deferasirox will be administered to achieve a ferritin < 100 ng/mL and, since it is approved for chelation and used regularly for this purpose as a standard of care, the dosing and schedule will be at the discretion of the treating clinician based on overall iron loading (ferritin), renal function, hepatic function, blood counts, and clinical condition / performance status. Contraindications include the following: Serum creatinine greater than two-times the upper limit of normal (ULN) or glomerular filtration rate (GFR) of less than 40 mL/min, poor performance status, high risk MDS, advanced malignancies, platelet count of less than 50,000, pregnancy, and/or known hypersensitivity to deferasirox.

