## 5.0 SUBJECT SELECTION

### 5.1 Inclusion Criteria

1. Capable of giving written informed consent prior to any study-specific procedures
2. Diagnosis of MDS as defined by the WHO diagnostic criteria (40) (**Appendix A**)
3. Have very low, low or intermediate risk disease by the IPSS-R (8) (**Appendix B**)
4. Baseline serum ferritin level  $\geq 100$  ng/mL
5. Have an ECOG performance status of 0-2 (41) (**Appendix C**)
6. Age  $\geq 18$
- 7.
8. Anemia defined as hemoglobin  $\leq 10.0$  g/dLHave adequate organ function, including:
  - a. Hepatic: Bilirubin  $\leq 1.5$  times upper limits of normal (ULN), alanine transaminase (ALT), and aspartate transaminase (AST)  $\leq 3.5$  times ULN
  - b. Renal: Serum creatinine  $\leq 1.5 \times$  ULN and estimated GFR  $> 40$  mL/min
9. Males and females with reproductive potential must agree to use medically approved contraceptive precautions during the study and for 3 months following the last dose of deferasirox\*
10. Females with childbearing potential\* must have had a negative urine or serum pregnancy test  $\leq 7$  days before the first dose of deferasirox and must also not be breastfeeding
11. Reliable and willing to make themselves available for the duration of the study and are willing to follow study procedures

\*Women of child-bearing potential, defined as all women physiologically capable of becoming pregnant, unless they are using effective methods of contraception during dosing of study treatment.

Effective contraception methods include:

- Placement of an intrauterine device (IUD) or intrauterine system (IUS)
- Barrier methods of contraception: Condom or Occlusive cap (diaphragm or cervical/vault caps) with spermicidal foam/gel/film/cream/ vaginal suppository
- Total abstinence or (when this is in line with the preferred and usual lifestyle of the subject). Periodic abstinence (e.g., calendar, ovulation, symptothermal, post-ovulation methods) and withdrawal are not acceptable methods of contraception
- Female sterilization (have had surgical bilateral oophorectomy with or without hysterectomy) or tubal ligation at least six weeks before taking study treatment. In case of oophorectomy alone, only when the reproductive status of the woman has been confirmed by follow up hormone level assessment
- Male sterilization (at least 6 months prior to screening). For female subjects on the study, the vasectomized male partner should be the sole partner for that subject

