#### **7.6.6 Hepatic Impairment**

Liver function tests should be monitored during the duration of the trial as indicated in **Table 2**.

Deferasirox can cause hepatic injury, fatal in some patients. Hepatic toxicity appears to be more common in patients greater than 55 years of age. Hepatic failure was more common in patients with significant comorbidities, including liver cirrhosis and multiorgan failure.

Consider dose modifications or interruption of treatment for severe or persistent elevations.

Patients with mild (Child-Pugh A) or moderate (Child-Pugh B) hepatic impairment may be at higher risk for hepatic toxicity. In a single dose (20 mg/kg) study in patients with varying degrees of hepatic impairment, deferasirox exposure was increased compared to patients with normal hepatic function. The average total (free and bound) AUC of deferasirox increased 16% in 6 patients with mild (Child-Pugh A) hepatic impairment, and 76% in 6 patients with moderate (Child-Pugh B) hepatic impairment compared to 6 patients with normal hepatic function. The impact of severe (Child-Pugh C) hepatic impairment was assessed in only 1 patient.

Avoid the use of deferasirox in patients with severe (Child-Pugh C) hepatic impairment. For patients with moderate (Child-Pugh B) hepatic impairment, the starting dose should be reduced by 50%. Closely monitor patients with mild (Child-Pugh A) or moderate (Child-Pugh B) hepatic impairment for efficacy and adverse reactions that may require dose titration.

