#### **7.6.9 Cytopenias**

There have been post-marketing reports (both spontaneous and from clinical trials) of cytopenias in patients treated with deferasirox. Most of these patients had pre-existing hematological disorders that are frequently associated with bone marrow failure. The relationship of these episodes to treatment with deferasirox is uncertain. In line with the standard clinical management of such hematological disorders, complete blood counts will be monitored regularly. Given the nature of this particular clinical trial in the setting of MDS patients, dose interruptions or modifications in patients who develop cytopenias or have worsening of cytopenias are at the discretion of the treating clinician.

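### The platelet limit and the hepatic-class dosing text each conflict with a discretion clause elsewhere, and it is unclear whether the renal limits bind on treatment

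*Combined protocol and SAP*

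**What the plan says.** **Contraindications.** Section 2.3 lists, among others, "Serum creatinine greater than two-times the upper limit of normal (ULN) or glomerular filtration rate (GFR) of less than 40 mL/min" and "platelet count of less than 50,000, pregnancy, and/or known hypersensitivity to deferasirox". Section 7.6.3 repeats the renal part: "Deferasirox is contraindicated in patients with an estimated GFR less than 40 mL/minute or serum creatinine greater than 2 times the age-appropriate upper-limit-of-normal".

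**Entry.** Section 5.1 and Appendix E require creatinine at or below 1.5 times ULN and an estimated GFR above 40. Section 5.2 and Appendix E exclude platelets at or below 50,000. The hepatic item uses bilirubin, ALT and AST only.

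**On treatment.**
- Renal, 7.6.3: "Deferasirox will be administered and dosed at the discretion of the treating clinician based on renal function as measured by serum creatinine and via the" GFR estimate.
- Cytopenias, 7.6.9: "dose interruptions or modifications in patients who develop cytopenias or have worsening of cytopenias are at the discretion of the treating clinician".
- Hepatic, 7.6.6: "Avoid the use of deferasirox in patients with severe (Child-Pugh C) hepatic impairment". The same section directs that the starting dose be halved in Child-Pugh B.
- Starting dose, 7.3: left to the clinician, who is to weigh ferritin, renal and hepatic function, blood counts and clinical condition. No exception is stated.

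**Removal.** Section 7.7 lists circumstances in which a patient may be taken off therapy. It includes a positive pregnancy test, disease progression and general safety-judgment clauses. It gives no GFR, creatinine, platelet or Child-Pugh limit.

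**The concern.** A patient can satisfy every entry criterion and later cross a limit that the protocol calls a contraindication. The reader then needs to know whether the limit still binds. For platelets, one section says the drug is contraindicated and another hands the decision to the clinician without mentioning the limit. For hepatic class, one section fixes an adjustment at the start of treatment and another leaves the starting dose open. The class itself is never recorded.

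Two clinicians in this trial could each follow the document and manage the same patient in opposite ways. The protocol treats the subject as serious: 7.6.10 reports gastrointestinal hemorrhage, including deaths, particularly in elderly patients with advanced hematologic malignancy or low platelets, and 7.6.3 reports fatal renal failure. Uneven handling at the renal and hepatic limits would also blur the secondary safety and tolerability endpoint.

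**Working it through.** No figure in the plan is at stake, so the check is to trace each limit through the protocol.

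| Limit | Entry (5.1, 5.2, Appendix E) | Written in 7.6 | Named in 7.7 | Explicit action for a patient already on drug |
|---|---|---|---|---|
| GFR below 40 | Yes (above 40 required) | Yes, 7.6.3 | No | No |
| Creatinine above 2 times ULN | Yes (at most 1.5 times ULN) | Yes, 7.6.3 | No | No |
| Platelets below 50,000 | Yes (50,000 or less excluded) | No | No | No |
| Child-Pugh C | Not by class | Yes, 7.6.6 | No | No |
| **Count** | **3 of 4** | **3 of 4** | **0 of 4** | **0 of 4** |

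The gap is therefore neither screening for laboratory limits nor their complete absence from the dosing section. It lies in what follows once treatment has begun, and in hepatic class at the start.

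**1. Platelets: 2.3 against 7.6.9.** Take a patient who enters at 51,000 and falls below 50,000 on a scheduled monthly CBC. Under 2.3, "platelet count of less than 50,000" is a contraindication, and the section does not restrict it to entry. Under 7.6.9 continuing unchanged is allowed, because interruption and modification are both optional. Section 7.6.9 neither repeats the limit nor refers back to it. Followed as written, 7.6.9 permits what 2.3 rules out.

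**2. Hepatic class: 7.6.6 against 7.3.** Section 7.6.6 attaches a fixed starting-dose adjustment to Child-Pugh B and avoidance to Child-Pugh C. Section 7.3 leaves the starting dose open and does not refer to 7.6.6. Four places could record the class before the first dose: the screening text in 7.3, Table 2, Appendix E and Appendix F. None does (0 of 4). The documents do not say how the bilirubin, ALT and AST limits map to a class, so it cannot be shown that the entry criteria exclude B or C.

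**3. Renal limits: within 7.6.3, and 7.6.3 with 7.7.** The contraindication and the discretion sentence concern the same two measures and stand in the same subsection. Two readings are open: discretion within the contraindication, or a contraindication for entry with discretion afterwards. The proteinuria paragraph that follows pairs discretion with an express statement that no contraindication arises from protein level. That favors the first reading, since it separates measures that carry a contraindication from one that does not. Section 7.7 pulls the other way: pregnancy, also on the 2.3 list, is carried into the removal criteria, and the laboratory limits are not. Neither reading is settled.

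**Comparison within 7.6.** The protocol does write on-treatment actions elsewhere. Section 7.6.5 covers severe rash and suspected Stevens-Johnson syndrome, and 7.6.8 and 7.6.11 cover severe hypersensitivity. Silence on the stated contraindications is therefore not a uniform drafting style.

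**The case against.** The case on the other side is substantial and rules out several stronger readings.

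- **That the limits are missing from the checklist or the dosing section.** A reader might infer this from 7.7. The table shows otherwise: Appendix E carries GFR, creatinine and platelets, at least as strictly as 2.3, and 7.6 itself contains the renal and Child-Pugh C limits.
- **That the renal text is contradictory.** Discretion exercised within a contraindication is an ordinary reading. This part is an ambiguity only.
- **That different sites would act differently.** Section 4.1 describes a single-center trial. Any divergence is between clinicians.
- **That the protocol's own rates size the problem.** The 37% with a creatinine increase (2.4) gives 0.37 × 25 = 9.25 patients. The 13.2% who stopped for abnormal laboratory values in the cited three-year trial (2.2) gives 0.132 × 25 = 3.3. The first is not restricted to rises above 2 times ULN, and the second pools all laboratory abnormalities. The 76% higher exposure in Child-Pugh B (7.6.6) is a single-dose result in 6 patients. None measures how often a limit would be crossed.

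The latitude in 7.6.9 is also deliberate: it cites pre-existing marrow disease, an uncertain relation to the drug and the MDS setting. That explains discretion in general, but it does not say that the platelet limit in 2.3 is set aside.

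Safeguards exist. Section 7.7 allows removal for an unacceptable safety risk, Section 10 has every patient's course reviewed weekly, and a DSMB that can stop the study reviews toxicity every six months. These reduce the risk of harm, although none tells a clinician which section governs an individual patient.

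The safety endpoint counts grade 3 and 4 non-hematologic events, so a platelet fall does not enter it directly. Finally, Sections 7.1, 7.2 and 11.2 refer to the manufacturer's directions, which may supply on-treatment actions. Their content is not in the documents, and 7.2 invokes them in the same sentence as clinician discretion.

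**Conclusion.** The point holds in three parts of unequal strength. Two are conflicts in the text: the platelet limit in 2.3 against 7.6.9, and the hepatic-class directions in 7.6.6 against 7.3, with no assessment of the class they depend on. The third is an ambiguity about whether the GFR and creatinine limits in 7.6.3 bind during treatment, which 7.7 leaves open by naming none of the four limits.

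The size in patients is unknown. The documents do not give the number who would cross a limit or who have Child-Pugh B or C impairment. The conclusion assumes that 2.3, which does not confine its contraindications to entry, can be read as applying throughout. If the sponsor means it for entry only, the platelet conflict disappears, but the protocol has to say so. The hepatic conflict does not depend on that assumption. The statistical decision rule for the primary endpoint is unaffected. This should be corrected because it concerns safety and costs little.

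**What to change.** 1. Reconcile 2.3, 7.6.3, 7.6.9 and 7.7 so that all four agree on whether the stated contraindications apply during treatment as well as at entry. State the agreed consequence once and refer to it from the other sections.
2. Reconcile 7.3, 5.1, 5.2 and Appendix E with 7.6.6. If the hepatic-class directions are kept, have the class recorded before the first dose and make the starting-dose text in 7.3 refer to 7.6.6.

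Which limits and actions apply is for the sponsor's clinicians to decide.

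The cost is protocol wording and a checklist line. Renal tests, liver tests and CBC are already scheduled in Table 2 and Appendix F. Recording hepatic class would be a new screening item. The downside is somewhat less latitude for clinicians.

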#### **7.6.4 Changes in Serum Ferritin**

Goal serum ferritin of < 100 ng/mL and deferasirox dose adjustment will be at the discretion of the treating clinician based on the monthly serum ferritin level (in addition to other variables as detailed above including renal function, hepatic function, blood counts, and clinical condition / performance status).

#### **7.6.5 Skin Disorders**

Rashes may occur during deferasirox treatment. For rashes of mild to moderate severity, deferasirox may be continued without dose adjustment, since the rash often resolves spontaneously. In severe cases, interrupt treatment with deferasirox. Reintroduction at a lower dose with escalation may be considered after resolution of the rash. Severe skin reactions, including Stevens-Johnson syndrome (SJS) and erythema multiforme, have been reported during deferasirox therapy. If SJS or erythema multiforme is suspected, discontinue deferasirox immediately and do not reintroduce deferasirox therapy.

#### **7.6.6 Hepatic Impairment**

Liver function tests should be monitored during the duration of the trial as indicated in **Table 2**.

Deferasirox can cause hepatic injury, fatal in some patients. Hepatic toxicity appears to be more common in patients greater than 55 years of age. Hepatic failure was more common in patients with significant comorbidities, including liver cirrhosis and multiorgan failure.

Consider dose modifications or interruption of treatment for severe or persistent elevations.

Patients with mild (Child-Pugh A) or moderate (Child-Pugh B) hepatic impairment may be at higher risk for hepatic toxicity. In a single dose (20 mg/kg) study in patients with varying degrees of hepatic impairment, deferasirox exposure was increased compared to patients with normal hepatic function. The average total (free and bound) AUC of deferasirox increased 16% in 6 patients with mild (Child-Pugh A) hepatic impairment, and 76% in 6 patients with moderate (Child-Pugh B) hepatic impairment compared to 6 patients with normal hepatic function. The impact of severe (Child-Pugh C) hepatic impairment was assessed in only 1 patient.

Avoid the use of deferasirox in patients with severe (Child-Pugh C) hepatic impairment. For patients with moderate (Child-Pugh B) hepatic impairment, the starting dose should be reduced by 50%. Closely monitor patients with mild (Child-Pugh A) or moderate (Child-Pugh B) hepatic impairment for efficacy and adverse reactions that may require dose titration.

#### **7.6.7 Auditory or Ocular Toxicity**

Auditory (decreased hearing) and ocular (lens opacities) disturbances have been reported with deferasirox treatment. Auditory and ophthalmic testing (including fundoscopy) is recommended before the start of deferasirox treatment and at regular intervals thereafter (every 12 months). If disturbances are noted, dose reduction or interruption may be considered.

#### **7.6.8 Hypersensitivity Reactions**

Cases of serious hypersensitivity reactions (such as anaphylaxis and angioedema) have been reported in patients receiving deferasirox, with the onset of the reaction occurring in the majority of cases within the first month of treatment. If reactions are severe, deferasirox should be discontinued.

#### **7.6.9 Cytopenias**

There have been post-marketing reports (both spontaneous and from clinical trials) of cytopenias in patients treated with deferasirox. Most of these patients had pre-existing hematological disorders that are frequently associated with bone marrow failure. The relationship of these episodes to treatment with deferasirox is uncertain. In line with the standard clinical management of such hematological disorders, complete blood counts will be monitored regularly. Given the nature of this particular clinical trial in the setting of MDS patients, dose interruptions or modifications in patients who develop cytopenias or have worsening of cytopenias are at the discretion of the treating clinician.

### 7.6.10 Gastrointestinal Ulceration, Hemorrhage, and Perforation

GI hemorrhage, including deaths, has been reported, especially in elderly patients who had advanced hematologic malignancies and/or low platelet counts. Nonfatal upper GI irritation, ulceration and hemorrhage have been reported in patients, including children and adolescents, receiving deferasirox. Monitor for signs and symptoms of GI ulceration and hemorrhage during deferasirox therapy and promptly initiate additional evaluation and treatment if a serious GI adverse event is suspected. The risk of gastrointestinal hemorrhage may be increased when administering deferasirox in combination with drugs that have ulcerogenic or hemorrhagic potential, such as nonsteroidal anti-inflammatory drugs (NSAIDs), corticosteroids, oral bisphosphonates, or anticoagulants. There have been reports of ulcers complicated with gastrointestinal perforation (including fatal outcome).

### 7.6.11 Hypersensitivity

Deferasirox may cause serious hypersensitivity reactions (such as anaphylaxis and angioedema), with the onset of the reaction usually occurring within the first month of treatment. If reactions are severe, discontinue deferasirox and institute appropriate medical intervention. deferasirox is contraindicated in patients with known hypersensitivity to deferasirox.

## 7.7 Criteria for Removal/Withdrawal

A patient may be discontinued from protocol-prescribed therapy under the following circumstances:

- Consent withdrawal at the patient's own request or at the request of their legally authorized representative;
- Any event that, in the judgment of the PI or designee, poses an unacceptable safety risk to the patient;
- If, in the PI or designee's opinion, continuation in the study would be detrimental to the patient's well-being;
- Significant deviation from inclusion/exclusion criteria, in the opinion of the PI or designee;
- A positive pregnancy test at any time during the study;
- An intercurrent illness that, in the judgment of the PI or designee, would affect assessments of the clinical status to a significant degree and requires discontinuation of therapy, or
- Completion of the study
- Evidence of disease progression to a higher stage of MDS or AML as defined by WHO criteria

Once the attending physician has met and discussed the decision with the patient and/or family member, the Notice of Withdrawal from a Research Study form (**Appendix H**) should be filled out.

- Once completed, the form should be faxed to FHCRC Research Coordinator at [contact].
- It is the responsibility of the PI or designee to complete the Notice of Withdrawal From a Research Study Form (see **Appendix H**) and fax it to the FHCRC Research Coordinator at [contact].

Study treatment is defined as "any activity involving a patient described in a protocol that is not part of their routine medical care". Patients that withdraw from study treatment will be asked permission to continue to record survival data up to the protocol-described end of the subject follow-up period as it is important to the integrity of the final study analysis.

Patients that are withdrawn from the protocol will not be replaced as this is intent to treat analysis.

